#### **4.1.5 Blinding and procedures for unblinding**

##### **4.1.5.1 Blinding**

This phase I trial will be performed according to an open-label, single arm design. It will recruit patients with relapsed and refractory NHL of B cell origin. This open-label trial will be handled in an open fashion by the sponsor throughout, *i.e.* also for the purpose of data cleaning and preparation of the analysis. The eCRF will contain information on the treatment and the dose.

##### **4.1.5.2 Procedures for emergency unblinding**

Not applicable.

#### **4.1.6 Packaging, labelling, and re-supply**

BI 836826 will be supplied in 10 mL vials containing 100 mg BI 836826. For details of packaging and the description of the label, refer to the ISF. Medication will be delivered to the investigator's pharmacy where the total dose per patient will be prepared upon request from the investigator.

For preparation of the BI 836826 infusion solution, the content of the vial of BI 836826 will be diluted in 0.9% sodium chloride. The content of several vials may be needed for administration of the requested dose. For further details, please refer to instructions included in the ISF.

#### **4.1.7 Storage conditions**

BI 836826 has to be stored in a limited access area at the temperature indicated on the trial drug label. If the storage conditions are found to be outside the specified range, immediately contact the local clinical monitor or the CRA as provided in the list of contacts. For more details on BI 836826, please refer to the IB ([c01715907-08](#)) and the ISF.

#### **4.1.8 Drug accountability**

Drug supplies, which will be provided by the sponsor or a CRO appointed by the sponsor, must be kept in a secure, limited access storage area under the storage conditions defined by the sponsor. A temperature log must be maintained to make certain that the drug supplies are stored at the correct temperature.

**Proprietary confidential information.**

**© 2016 Boehringer Ingelheim International GmbH or one or more of its affiliated companies. All rights reserved.**

This document may not - in full or in part - be passed on, reproduced, published or otherwise used without prior written permission.

The investigator and/or pharmacist will receive the investigational drugs delivered by the sponsor when the following requirements are fulfilled:

- approval of the study protocol by the IRB / ethics committee
- availability of a signed and dated clinical trial contract between the sponsor and the Head of Trial Centre
- approval/notification of the regulatory authority, *e.g.* competent authority
- availability of the curriculum vitae of the principal investigator
- availability of a signed and dated clinical trial protocol or immediately imminent signing of the clinical trial protocol

The investigator and/or pharmacist must maintain records of the product's delivery to the trial site, the inventory at the site, the use for each patient, and the return to the sponsor or alternative disposition of unused product. The investigator / pharmacist will maintain records that document adequately that the patients were provided the doses specified by the CTP and reconcile all investigational product received from the sponsor.

## **4.2 CONCOMITANT THERAPY, RESTRICTIONS, AND RESCUE TREATMENT**

### **4.2.1 Rescue medication, emergency procedures, and additional treatment**

#### **4.2.1.1 Rescue medication**

Rescue medication in term of an antidote to reverse the action of BI 836826 is not available. Potential side effects of BI 836826 have to be treated symptomatically.

#### **4.2.1.2 Supportive care**

Patients should receive supportive care according to local guidelines regarding treatment of infusion-related reactions ([section 4.1.4.2](#) and [section 5.2.5.1](#)), infections, blood product support, analgesics, skin and mouth care, etc.

In the case of a tumour lysis syndrome, supportive therapy including rasburicase may be used as clinically indicated at the investigator's discretion ([section 5.2.3.2](#)).

#### **4.2.1.2.1 Antibiotics and Antivirals**

Prophylactic antibiotics and antivirals are allowed. For patients who are considered to have an increased risk for herpes and/or pneumocystis jiroveci infections, the prophylaxis is mandatory, unless medically contraindicated (see below). For patients who are considered to have an increased risk for other infections, prophylactic therapy is recommended, unless medically contraindicated.

Prophylactic antiviral therapy is mandatory for patients with a history of recurrent herpes virus infections, herpes infection during previous anti-lymphoma therapy, neutropenia and/or low CD4+ cell counts (<200 cells/ $\mu$ l), *e.g.* acyclovir 400 mg three times a day orally.

**Proprietary confidential information.**

**© 2016 Boehringer Ingelheim International GmbH or one or more of its affiliated companies. All rights reserved.**

This document may not - in full or in part - be passed on, reproduced, published or otherwise used without prior written permission.

Prophylactic antiviral therapy (*e.g.* nucleoside reverse transcriptase inhibitor) and/or monitoring of hepatitis B DNA in the blood is recommended for patients with a history of hepatitis B infection.

Prophylaxis against pneumocystis jiroveci, *e.g.* oral trimethoprim/sulfamethoxazole 800 mg/160 mg every other day is mandatory to patients who are considered at increased risk, *e.g.* patients with low CD4+ cell counts (<350 cells/ $\mu$ l).

Infections should be treated early, *i.e.* at the first clinical signs, with a broadband antibiotics, and other agents (antivirals, antifungals, growth factors), as deemed appropriate by the investigator. The investigators are expected to apply treatment according to local guidelines/standard.

#### 4.2.1.2.2 Growth factors

The use of growth factors such as granulocyte colony stimulating factor (G-CSF) will be allowed during therapy. However, growth factors are not allowed at inclusion and should be avoided, if patient's condition allows, in the first treatment weeks for better assessment of safety parameters.

Prophylactic antibiotics and antiviral drugs are allowed during therapy.

#### 4.2.1.3 Concomitant medication

All concomitant therapies to provide adequate care may be given as clinically necessary, unless given as anti-lymphoma therapy. All concomitant treatments should be recorded in the eCRF except for vitamins or nutrient supplements. Trade name, indication and dates of administration of concomitant therapies will be documented. For parenteral nutrition during the trial, the components need not to be specified in detail. It should just be indicated as 'parenteral nutrition'. If a patient needs general anaesthesia, it will be sufficient to indicate 'general anaesthesia' without specifying the details.

Concomitant therapy should be recorded in the eCRF during the screening and treatment period, starting at the date of signature of informed consent, and ending at the EOT visit. After the EOT visit, only concomitant therapy indicated for treatment of an adverse event has to be reported or if given as new anti-lymphoma therapy.

CMV reactivation during treatment should be treated according to local standards or available guidelines ([R10-4431](#)).

### 4.2.2 Restrictions

#### 4.2.2.1 Restrictions regarding concomitant treatment

Prior therapies for lymphoma must have been discontinued at least of two weeks before the first administration of the trial drug (see exclusion criteria [section 3.3.3](#) for details) and the patient must have recovered from all clinically relevant reversible toxicities. A time interval

Proprietary confidential information.

© 2016 Boehringer Ingelheim International GmbH or one or more of its affiliated companies. All rights reserved.

This document may not - in full or in part - be passed on, reproduced, published or otherwise used without prior written permission.

of at least four weeks must have elapsed from the last administration of any other investigational treatment for NHL to the first administration of BI 836826.

No anti-neoplastic therapy concomitantly is allowed.

No other investigational therapy concomitantly is allowed.

Additional glucocorticoid medications may be used as clinically indicated to treat infusion-related reactions at any dose. Short term systemic glucocorticoid for lung disease (asthma or COPD) may be used. Daily oral steroid treatment may be administered at doses equivalent to prednisolone 10 mg per day. All other indications for steroids have to be discussed and agreed upon between investigator and sponsor.

Immunoglobulins may not be used within four weeks prior to the first trial infusion and two weeks after the last infusion of BI 836826.

#### **4.2.2.2 Restrictions on diet and life style**

No restrictions apply with regard to diet or life style.

### **4.3 TREATMENT COMPLIANCE**

BI 836826 will be administered as a single intravenous infusion under supervision of the investigator or dedicated clinic personnel.

Any discrepancies will be explained in the CRF by the investigator or his/her deputy.

## **5. VARIABLES AND THEIR ASSESSMENT**

### **5.1 EFFICACY**

#### **5.1.1 Endpoints of efficacy**

The efficacy endpoints will be assessed at the time points specified in the [flowcharts](#). Efficacy endpoints will be secondary or further endpoints in this trial.

Secondary endpoints of efficacy are:

- Tumour size reduction (lymph nodes, spleen and liver nodules) defined as best % change from baseline in SPD (all lymph nodes, only spleen nodules, only liver nodules) from CT scan data
- Best overall response according to Standardized or Revised Response Criteria for Malignant Lymphoma ([R04-1585](#)) (see [section 5.1.2.2](#))
- Progression free survival
- Failure free survival

#### **5.1.2 Assessment of efficacy**

##### **5.1.2.1 Tumour size**

Tumour size of lymph nodes, spleen and liver, nodules will be measured throughout the trial. Nodal, spleen, liver and other locations amenable to clinical examination should be assessed at indicated time point as well as by CT scans (see [flowcharts](#)). The tumour size of the lymph nodes will be measured as sum of products of diameter (SPD) of two perpendicular dimensions for up to 6 indicator lesions identified at baseline CT scan. Spleen and liver will be described, if considered enlarged at baseline by physical examination or CT scan. If nodules are present in spleen and/or liver, the diameter of these will be measured in two perpendicular dimensions. The change in SPD, spleen and liver nodules will be compared to baseline and will be listed by time point.

CT scan description will rely on the description by the local radiologist at the investigational site.

### 5.1.2.2 Assessment and definition of overall best response

CT scan will be required for response assessment. CT scan will be performed at screening, at week 13 and week 25. A CT scan may be performed at end of treatment if therapy terminates earlier, *e.g.* to document progression. Bone marrow biopsy/aspirate may be performed as indicated by the investigator, but it will not be mandatory. The best response at any of CT scans done will be overall best response. Response will be assessed according to the standardized response criteria from 1999 ([R04-1585](#)).

#### 5.1.2.2.1 Complete remission

Complete remission (CR) requires complete disappearance of all evidence of disease.

1. Complete disappearance of all detectable clinical and radiographic evidence of disease and disappearance of all disease-related symptoms if present before therapy and normalization of those biochemical abnormalities definitely assignable to NHL
2. Absence of significant lymphadenopathy, *i.e.* lymph nodes  $\leq 1.5$  cm at the greatest transverse diameter for nodes  $> 1.5$  cm before therapy. Nodes between 1.1 and 1.5 cm at the long axis and  $> 1$  cm at the short axis before therapy must have decreased to  $\leq 1.0$  cm in their short axis
3. Spleen, if enlarged by CT scan before therapy, must have regressed in size and must not be palpable on physical examination
4. Other organs considered enlarged before therapy due to lymphoma must have regressed in size
5. Bone marrow aspirate and biopsy demonstrate absence of residual disease (if performed)

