The Ann Arbor staging system is used to describe disease involvement in NHL ([R10-6400](#) and [appendix 10.4](#)). The disease stage is determined by computerized tomography (CT) scanning and bone marrow biopsy/aspirate. Extra-nodal disease as well as B symptoms (*i.e.* unexplained fever, night sweats or weight loss) further describes the disease status at diagnosis. The addition of F-deoxyglucose-positron emission tomography (PET) scanning for staging and early response evaluation can identify patients with DLBCL who are likely to achieve a durable response ([R10-6359](#)). Combination of [F]Fluorodeoxyglucose-positron emission tomography (PET) with computer tomography (CT) scanning has been reported to be superior to PET alone ([R10-6358](#)). The role of PET/CT performed during the treatment of DLBCL to guide eventual therapy modifications to improve outcome is less clear due to non lymphoma specific PET positivity ([R10-6313](#)). The role of PET scanning for the indolent lymphomas and for refractory setting is more uncertain ([R10-1462](#)).

Risk assessment at diagnosis with the international prognostic index (IPI) has been clinically useful for the patients with DLBCL ([R10-6349](#)). The index encompasses of 5 parameters: age >60 years, stage III or IV, ≥2 extranodal sites, performance status ≥2 and lactate dehydrogenase (LDH) above upper limit of normal as prognostic factors. Recently, an

Proprietary confidential information.

© 2016 Boehringer Ingelheim International GmbH or one or more of its affiliated companies. All rights reserved.

This document may not - in full or in part - be passed on, reproduced, published or otherwise used without prior written permission.

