## **3.2    DISCUSSION OF TRIAL DESIGN, INCLUDING THE CHOICE OF CONTROL GROUP**

The primary objective of this trial is to determine the MTD. The most important secondary objective is to assess the safety of BI 836826. This can be achieved by an open-label, single arm trial design without a control group.

The investigational drug BI 836826 will be administered as monotherapy. At the lowest dose cohorts, single patients are to be enrolled to limit the number of patients who are receiving doses of the drug which may not exert a relevant pharmacodynamic effect in humans. Stipulated by drug related adverse events CTCAE grade 2 or higher, cohorts of single patients will be expanded to cohorts of at least 3 patients as described in section [3.1](#), and the trial design will follow a standard 3+3 design with dose-escalation and de-escalation. According to the interim safety analysis of the trial results, the MTD was defined for Caucasian patients to be 100 mg. Once the MTD has been defined for Asian patients the enrollment will be stopped. Given the recent safety signals at 100 mg, the current expansion cohort at MTD of 100 mg will be closed for enrollment after having enrolled 4 patients from S Korea, and a new, small cohort will be open to test the 50 mg and 75 mg dose in Korean patients.

At screening, blood samples are drawn, a physical examination and a routine CT scan are performed, and the patient is evaluated for eligibility in the trial. Bone marrow aspirate/biopsy may be performed at the discretion of the investigator. In case a bone marrow aspirate/biopsy has been performed after the latest therapy before this trial, it should be recorded.

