**Proprietary confidential information.**

**© 2016 Boehringer Ingelheim International GmbH or one or more of its affiliated companies. All rights reserved.**

This document may not - in full or in part - be passed on, reproduced, published or otherwise used without prior written permission.

Clinical disease status will be assessed at screening, at the administration of the first and the last of the 4 infusions and 3 weeks after the last infusion of a respective course with physical examination, clinical assessment of the B-NHL, and blood samples. CT scans in this trial will be performed in accordance with published guidelines for response evaluation in lymphoma ([R04-1585](#)) and correspond to the use in clinical practice ([section 5.1.2.2](#)). A CT scan will be done prior to treatment (may be performed up to 8 weeks (preferably 4 weeks) prior to first infusion), after 2 courses of treatment, (*i.e.* at week 13 +/- window), and just before the end of treatment (EOT) visit (*i.e.* week 25 +/- window). If the CT scans are not possible or available, magnetic resonance imaging can be used instead. However the same imaging methods should be used consistently throughout the trial. Bone marrow examination, PET scan and additional CT scans will be performed at the discretion of the investigator. Results of CT scan, optional PET scan or bone marrow examination performed during the conduct of the trial should be reported in the eCRF. After the EOT visit which may occur at the latest at week 26, the patient will enter the follow-up phase. During the follow-up phase, disease status evaluations (physical examination, clinical assessment of lymphoma, and blood samples) should be performed at least every 6 weeks until 6 months after the EOT visit, administration of new anti-lymphoma therapy or death, whatever occurs first. More frequent visits may be indicated, *e.g.* for follow-up of laboratory parameters or adverse events which have not been resolved at the EOT visit.

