#### 3.3.2 Inclusion criteria

1. Patients with relapsed or refractory non-Hodgkin lymphoma of B cell origin (mature B cell lymphoma according to WHO) not considered candidates for intensive anti-lymphoma therapy
2. Patients must have either aggressive NHL and received at least one prior anti-CD20 containing immunochemotherapy or indolent NHL and received anti-CD20 therapy and at least two prior therapies (see [appendix 10.2](#))
  - a. Patients with aggressive NHL who have received at least one prior anti-CD20 containing immunochemotherapy and have
    - i. relapse/progression and is not considered a candidate for high-dose immunochemotherapy with autologous stem cell support or allogeneic transplantation
    - ii. relapse/progression after high-dose immunochemotherapy with autologous stem cell support
    - iii. relapse/progression after allogeneic stem cell transplantation if without

Proprietary confidential information.

© 2016 Boehringer Ingelheim International GmbH or one or more of its affiliated companies. All rights reserved.

This document may not - in full or in part - be passed on, reproduced, published or otherwise used without prior written permission.

immunosuppression for at least 8 weeks and no evidence of active GvHD (this criterion applies only for the expansion cohort)

- b. Patients with indolent NHL who have received anti-CD20 therapy and at least two prior therapies and have
  - i. relapse/progression and is not considered a candidate for high-dose immunochemotherapy with autologous stem cell support or allogeneic transplantation
  - ii. relapse/progression after high-dose immunochemotherapy with autologous stem cell support
  - iii. relapse after allogeneic stem cell transplantation if without immunosuppression for at least 8 weeks and no evidence of active GvHD (this criterion applies only for the expansion cohort)
- 3. Measurable disease on CT scan with involvement of at least one clearly demarcated lesion  $\geq 2$  cm or two or more clearly demarcated lesions of  $>1.5$  cm at longest diameter (this criterion applies only for the expansion cohort)
- 4. Relapse or progression of disease with an indication for therapy as per investigator's judgement
- 5. Life expectancy of  $\geq 3$  months as per investigator's judgement
- 6. ECOG Performance Status 0 or 1 (see appendix [10.3](#))
- 7. Age  $\geq 18$  years
- 8. Written informed consent which is consistent with ICH-GCP guidelines and local legislation

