5.2.2 Other Secondary endpoints

Tumour size reduction (indicator lesions, spleen and liver nodules)

Tumour size reduction of indicator lesions, spleen nodules and liver nodules will be analysed separately as secondary endpoints as follows:

Tumour size reduction of indicator lesions will be analysed as secondary endpoint “Best % change from baseline in SPD” from imaging data.

Tumour size reduction of liver nodules will be analysed as secondary endpoint “Best % change from baseline in SPD” from imaging data.

Tumour size reduction of spleen nodules will be analysed as secondary endpoint “Best % change from baseline in SPD” from imaging data. Best overall response (according to investigator assessment):

Response will be assessed according to the Standardized or Revised Response Criteria for Malignant Lymphoma from 1999 ([[R04-1585](#)]). Each patient will be assigned to one of the

following categories:

- complete remission (CR)
- complete remission unconfirmed (CRu)
- partial remission (PR)
- stable disease (SD)
- progressive disease (PD)

Best overall response (CR, CRu, PR, SD, PD in this order) is defined as the best overall response obtained since the start of study treatment. Best overall response will be evaluated in two different ways: first, all responses as documented by the investigator (independent of the assessment procedure) will be evaluated. In a further analysis, only disease evaluations for which imaging data are available in the eCRF will be evaluated. In case PD is captured by the investigator, the response PD will be always considered as PD, independent whether imaging data is available at this timepoint or not. For both evaluations only response assessments prior to any further NHL therapy and until PD will be taken into account. For the calculation of the date of response: if patients would have their examinations contributing to the disease assessment over a number of days, the earliest date of the multiple examinations will be considered.

Progression free survival (PFS):

PFS is defined as the time from first administration of study medication until disease progression or death, whatever occurs first.

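### A patient with marrow involvement recorded before treatment can be counted as CR without a repeat marrow, and neither SAP best-response evaluation would show it

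*Protocol*

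**What the plan says.** **Required examination.** Protocol 5.1.2.2 states: "CT scan will be required for response assessment". On marrow, the same section states: "Bone marrow biopsy/aspirate may be performed as indicated by the investigator, but it will not be mandatory". Protocol 3.2 says the same of screening ("Bone marrow aspirate/biopsy may be performed at the discretion of the investigator") and of the trial period ("Bone marrow examination, PET scan and additional CT scans will be performed at the discretion of the investigator"). No section makes an exception for a patient whose marrow is known to be involved.

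**CR.** The opening sentence of Protocol 5.1.2.2.1 asks that every sign of disease has gone. Five criteria follow. The first covers clinical and radiographic findings, symptoms, and biochemistry attributable to the lymphoma. The second to fourth cover nodes, spleen and other organs. The fifth is "Bone marrow aspirate and biopsy demonstrate absence of residual disease (if performed".

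**CRu.** Protocol 5.1.2.2.2 requires either a remaining nodal mass that has shrunk by over 75% in SPD or an indeterminate marrow result. A marrow that was not examined is neither.

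**SAP 5.2.2.** One evaluation takes every response the investigator documented, whatever the procedure. In the other, "only disease evaluations for which imaging data are available in the eCRF will be evaluated", apart from PD, which always counts. Neither carries a marrow condition.

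**Entry.** Inclusion criterion 3 in Protocol 3.3.2 (one larger lesion, or "two or more clearly demarcated lesions of" a smaller stated size) applies only to the expansion cohort, which is now closed.

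**The concern.** CR is the top category of best overall response. The protocol's own background treats marrow as a part of staging separate from CT: "The disease stage is determined by computerized tomography (CT) scanning and bone marrow biopsy/aspirate". Yet the fifth criterion lapses when no marrow is done, so a site of disease already on record can go unchecked in a patient reported as free of disease. Two patients in the same state could also be classified differently, depending only on whether the investigator repeated the marrow. The CR tables would not separate a CR with a cleared marrow from one with an unexamined marrow. At stake is how the CR count is read. The MTD and DLT results are not touched.

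**Working it through.** The plan gives no figure on this point, so the main check is to follow one patient through the text.

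**Step 1. The patient.** The marrow is recorded as involved before treatment. On CT, nodes and organs return to the sizes that the CR criteria require. Symptoms and lymphoma-related biochemistry resolve. No repeat marrow is done.

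| Rule | Result |
|---|---|
| CR criterion 1 | met |
| CR criteria 2 to 4 | met |
| CR criterion 5 | does not apply, as no marrow was performed |
| CRu | not reached: no remaining mass, no indeterminate marrow |
| SAP 5.2.2, all investigator responses | CR |
| SAP 5.2.2, imaging available | CR |

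**Step 2. Which rate moves.** The remission rate in Protocol 7.3.2.3 is CR + CRu + PR. PR in 5.1.2.2.3 needs a fall of at least 50% in nodal SPD, no growth elsewhere and no new site. A patient with nodal disease who meets CR criteria 1 to 4 would generally meet this too. Moving such a patient from CR to PR lowers the CR count by one and leaves the remission rate as it was.

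The exception is a patient with no measurable nodal disease, who has no nodal SPD on which to show PR. Such patients can enter the escalation cohorts, because inclusion criterion 3 does not apply there, and Protocol 3.1 describes the 50 mg and 75 mg Korean cohorts as escalation cohorts.

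**Step 3. Size of one patient.** Inputs: 37 Caucasian patients in the escalation and 4 Korean patients at 100 mg (SAP 3); 41 enrolled so far and up to 12 more (Protocol 7.6).

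- Check of the total: 37 + 4 = 41, and 41 + 12 = 53, which is the protocol's approximate figure.
- SAP 6.1 reports all Korean patients together. That is at most 12 + 4 = 16, so one patient is 1/16 = 6.3 points.
- Over all patients, one patient is 1/53 = 1.9 points.
- SAP 6.1 also reports each dose cohort. In a new cohort of 3 to 6, one patient is 1/3 = 33.3 to 1/6 = 16.7 points, so these cohorts are better read as counts.

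The documents give neither the frequency of marrow involvement at baseline nor that of repeat examination, so the number of affected patients cannot be estimated.

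**The case against.** The best defence is textual. The opening sentence of the CR definition demands that all evidence of disease has gone, and a recorded positive marrow is such evidence. The qualifier in criterion 5 does not say whether it refers to a marrow at baseline or at response; if it means baseline, a patient with a positive marrow and no repeat would fail criterion 5. The protocol also applies the 1999 response criteria, whose text is not in the documents. This shows that a stricter reading is possible, but it does not settle which reading investigators will use. Criterion 1 does not name the marrow, and the ordinary reading of criterion 5 waives an examination that was not done.

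A second defence is that optional marrow is stated openly and consistently, in a phase I trial whose best-response endpoint is secondary and untested (Protocol 5.1.1 and 7.2). That stands, and it limits the weight of the point.

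A reader might infer three stronger things that the documents do not support:

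- **That imaging cannot show marrow disease.** No section says so, and Protocol 3.2 allows MRI as a substitute and optional PET. The point does not need this premise: nothing requires the marrow to be checked by any means.
- **That a patient with marrow disease only could be CR with no change at all.** Criterion 1 must still be met, and inclusion criterion 4 requires relapse or progression with an indication for therapy. Such a patient would need to have no symptom, clinical sign or attributable biochemical abnormality. The documents do not show that one exists.
- **That the remission rate is materially inflated.** Step 2 shows that, for nodal disease, the shift is mostly between CR and PR.

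**Conclusion.** The point holds in a limited form. As written, the rules allow CR to be counted in a patient with recorded marrow involvement and no repeat marrow, and the SAP would not reveal it. This is a stated rule that can give the wrong category, not merely missing detail. It affects mainly the CR count. The remission rate is exposed only through patients without measurable nodal disease.

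One patient is worth 6.3 points among all Korean patients and 1.9 points overall. This assumes that the maximum of 12 further patients is enrolled and that every enrolled patient is in the denominator; with fewer patients, each counts for more. The conclusion also rests on the ordinary reading of criterion 5. Correcting it is a cheap improvement, and no dose conclusion depends on it.

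**What to change.** Amend SAP 5.2.2, for analysis only, with no change to treatment decisions and no required biopsy:

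1. Where the marrow was recorded as involved before treatment, count CR as confirmed only if a repeat marrow is negative.
2. Tabulate every CR without that confirmation on its own line, *CR, marrow not confirmed*. Include patients whose marrow status before treatment is unknown.
3. If these patients are to go into CRu instead, add an unexamined marrow to the features in Protocol 5.1.2.2.2. The present two features would not admit them.
4. Show patients with neither CT-measurable disease at baseline nor a repeat marrow as not evaluable for remission, and keep them in the denominator. Add that category to the response list in SAP 5.2.2; the SAP abbreviation list already has NE, but the response list does not use it. Limit it to the best-response tables, so that the PFS and FFS censoring rules stay as they are.

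The data are largely in hand: Protocol 3.2 asks for a marrow done after the latest therapy to be recorded, and for marrow results during the trial to be reported in the eCRF. The cost is SAP wording and one more table line, with protocol wording only if the CRu route is chosen. The CR count may be lower.
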